## 5.

# STUDY SYNOPSIS **Study Title** An assessment of the impact of **CONT**rast **EN**hance**D** Spectral Mammography (CESM) on patient management and comparison with MRI (CONTEND Study) Internal ref. no. RADIOL/2015/CONTEND **Study Design** The aim of this pilot study is to establish the Contrast Enhanced Spectral Mammography (CESM) technique and study procedures. Results of this pilot and feedback from staff will inform Phase 2 of the study which will be a larger, multi-centre, randomised control trial. The study will be undertaken by members of the Cambridge Breast Unit (CBU) at Addenbrooke's Hospital, Cambridge using CESM technology provided by GE Healthcare as an upgrade to the GE Senographe Essential digital mammography system. This technology is already established throughout the world and has FDA approval and is CE marked. This will be a randomised, sequential cohort study. Following standard mammography and ultrasound all women with lesions of suspicion 3, 4 or 5 will be randomised to either receive CESM in addition to their assessment procedure or to receive usual care. Sealed envelopes will be held at CBU reception desk containing either 'CESM' or 'Usual Care' and one will be selected at random to determine to which arm of the study the woman is allocated. After providing informed consent, those women randomised to receive CESM will undergo the procedure either during the same clinic visit or on a day following the initial clinic visit. This will be dependent upon clinic time and staff availability and the woman's own preferences / circumstances. The index lesion and any additional disease detected by CESM will be biopsied as appropriate and results will be discussed at the multidisciplinary meeting (MDT). For those with biopsy confirmed disease a decision will be made at that meeting regarding conservation surgery, mastectomy or neo-adjuvant therapy. For those with benign disease

confirmed by core biopsy standard care will be followed.

MRI will be performed on appropriate women in line with standard practice. Additional disease detected by MRI will be biopsied if this will influence patient management. Biopsies will be undertaken using either ultrasound or MRI guidance. These cases will be discussed at the MDT and a decision made regarding conservation surgery, mastectomy or neo-adjuvant therapy.

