The pathway for women randomised to receive usual care will be the same as for those randomised to receive CESM, excluding the CESM procedure, i.e. they will undergo biopsy during their initial clinic visit and results will be discussed at the MDT where a decision regarding their future management will be made.

A flowchart illustrating patient pathways during the CONTEND Study can be found in Appendix I of this document.

A proforma will be used for each case to record patient pathway, results of biopsies and MDT patient management decisions.

Staff will be asked to provide feedback on patient acceptability and ease of undertaking the CESM procedure. They will also be asked to record any incidents of note, e.g. patient related problems; impact on clinic; issues with equipment. Time taken to undertake the examination will be recorded.

In order to compare the diagnostic accuracy of CESM with MRI, CESM images and MRI images will be anonymised and read by different readers - CESM images will be reported without the knowledge of the MRI results and vice versa. Mammography and ultrasound images will be available. A completed report on a proforma will be the basis for statistical analysis.

Histopathology data collected following surgery or from core biopsy if surgery is not undertaken and will be used as the gold standard for measurement of tumour size and extent of disease. If the patient is having primary drug therapy, tumour size will be determined from the mammogram.

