# **Study Participants**

Women attending CBU who have lesions of suspicion 3, 4 or 5 following routine mammography and ultrasound.

50 patients with successful CESM examinations will be required to establish the technique, study procedures and to provide sufficient data to inform further study. It is estimated, due to randomisation procedure, approximately 100 patients will need to be recruited in order to obtain this number.
Recruitment to the study is planned to run for 12 months or until sufficient number of participants has been accrued. The study will end once data analysis is complete.
To assess the impact the addition of CESM has on patient management.
To compare the sensitivity and specificity of CESM with MRI.
The detection of additional disease by CESM that changes patient management. Analysis will be undertaken to determine the impact of CESM on patient management decisions (actual or hypothetical). These will be extracted from details recorded on the proforma.
Secondary endpoints are the sensitivity and specificity of CESM and MRI on a per lesion basis – including comparison of the maximum dimension of the index tumour – as assessed by independent readers and compared with surgical histopathology.
The efficacy of each technique at detecting additional lesions and the number of false positives identified by each will also be determined. False positives will be confirmed through follow up at 6 months.
Analysis of results will inform further study, e.g. sample size and power calculations, and will include an assessment of clinical technique and study procedures from staff questionnaires.

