### 8.3.3 Exclusion Criteria

The presence of any of the following will preclude patient inclusion:

- Known or suspected pregnancy
- Breast implant
- Previous breast cancer
- Known renal impairment
- History of anaphylactoid or anaphylactic reaction to any contrast media

- Contrast media within 24 hours prior to CESM
- Commencement of neo-adjavant chemotherapy, hormone treatment, radiotherapy or surgery for this episode

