### Comparison of CESM and MRI

CESM images and MRI images will be anonymised and read by different readers - CESM images will be reported without the knowledge of the MRI results and vice versa. Mammography and ultrasound images will be available. A completed report on a proforma will be the basis for statistical analysis.

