# 8.4.2 Definition of End of Study

The study will end once the last patient recruited has undergone surgery and the surgical histopathology results are available.

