# 10.2 Analysis of Endpoints

Data from all eligible subjects will be included in the analyses. These will be patients for whom we have data from MRI, CESM and surgical histopathology.

Statistical significance of differences between CESM and MRI will be calculated using McNemar's test . Receiver operating characteristic (ROC) curves will be constructed for both imaging modalities.

Agreement between maximum lesion diameter based on CESM and MRI or CESM and histopathology will be expressed in Bland-Altman plots.

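### Women who have drug therapy and then surgery fall under two size references, and section 10.2 names no MRI–histopathology agreement plot

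*Protocol*

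**What the plan says.** **Size reference.** The synopsis (section 5, Study Design) makes histopathology the gold standard for tumour size and extent, from surgery or, failing surgery, from core biopsy. It then adds: "If the patient is having primary drug therapy, tumour size will be determined from the mammogram". The size endpoint is worded differently. The synopsis endpoint, section 8.2 and the Analysis paragraph of section 8.4 all take the maximum dimension of the index tumour on CESM and MRI "as assessed by independent readers and compared with surgical histopathology". None of the three mentions drug therapy.

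**Who is analysed.** Section 10.2 defines the eligible subjects: "These will be patients for whom we have data from MRI, CESM and surgical histopathology". It does not mention treatment before surgery.

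**Which agreement is plotted.** Section 10.2 states: "Agreement between maximum lesion diameter based on CESM and MRI or CESM and histopathology will be expressed in Bland-Altman plots". MRI against histopathology is not named.

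**What the readers see.** Section 8.4 (Comparison of CESM and MRI) says: "Mammography and ultrasound images will be available". The sentence applies to both sets of readers.

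**The concern.** The first issue is that one woman can have two reference sizes. If she has drug therapy and then surgery, the synopsis points to her mammogram, while the endpoint and section 10.2 point to her surgical specimen. Two analysts could each follow the Protocol and enter different values for her in the same Bland-Altman plot.

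The second issue is that the list of plots in 10.2 is narrower than the endpoint it serves. The endpoint judges both techniques against surgical histopathology, but only CESM gets a plot against it. The pilot is meant to inform a larger trial comparing CESM with MRI (section 6, Rationale), so the spread of MRI's sizing error is a quantity the next stage would want.

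**Working it through.** **1. Can a woman fall under both size rules?**

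- The MDT may choose drug therapy after the study imaging: "a decision will be made at that meeting regarding conservation surgery, mastectomy or neo-adjuvant therapy" (synopsis). The synopsis gives the same choice for cases discussed after MRI.
- The exclusion removes only women already under treatment: "Commencement of neo-adjavant chemotherapy, hormone treatment, radiotherapy or surgery for this episode" (section 8.3.3). A woman sent for drug therapy at a later MDT stays in.
- The study waits for surgery: "The study will end once the last patient recruited has undergone surgery and the surgical histopathology results are available" (section 8.4.2).
- If she has had MRI, CESM and surgery, she meets the rule in 10.2.

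So the overlap is possible. The Protocol does not say how many women it would involve.

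**2. How good is each reference for her?**

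*Mammogram.* It is not independent of the readings, because both sets of readers may consult it. Section 6 (Summary of literature) reports, for the second of the two direct comparisons, significant differences between mammography and both CESM and MRI in the correlation of size measurements. A mammographic size may also be missing. In the two cited studies mammography detected:

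| Cited study | Detected | Not detected |
|---|---|---|
| First | 42/52 = 80.8% | 10/52 = 19.2% |
| Second | 66/80 = 82.5% | 14/80 = 17.5% |

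*Surgical specimen.* The exclusion and the order of the pathway place the images before treatment, while the specimen is measured after it. Any change in the tumour during treatment would be counted as imaging error.

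**3. What do the two named plots give for MRI?**

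Let C, M and H be the sizes on CESM, MRI and histopathology in the same women. Then M − H = (C − H) − (C − M).

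- *Mean bias:* bias(M − H) = bias(C − H) − bias(C − M). This follows from the two plots.
- *Spread:* let a = SD(C − H), b = SD(C − M), m = SD(M − H), and r = the correlation between the errors C − H and M − H. Then b² = a² + m² − 2ram, so for b ≥ a, m = ar + √(a²r² + b² − a²). The plots give a and b but not r, so m and the limits ±1.96m stay open.

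Illustration only; the Protocol gives no SDs or correlations, so a, b and r are assumed:

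| a (mm) | b (mm) | r | m (mm) | MRI limits (mm) |
|---|---|---|---|---|
| 5 | 5 | 0.25 | 2.5 | ±4.9 |
| 5 | 5 | 0.5 | 5.0 | ±9.8 |
| 5 | 7 | 0.25 | 6.31 | ±12.4 |
| 5 | 7 | 0.5 | 8.00 | ±15.7 |

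The gap between the two correlations is 9.8 − 4.9 = 4.9 mm in the first pair and 15.7 − 12.4 = 3.3 mm in the second.

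For comparison, the 95% CI half-width of one directly plotted limit is 1.96·SD·√(1/n + 1.96²/(2(n − 1))). This is 0.477·SD at n = 50 and 0.679·SD at n = 25. With SD 5 mm the full width is 4.8 mm and 6.8 mm. With SD 8 mm it is 7.6 mm and 10.9 mm.

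Section 10.1 plans about 100 women to give 50 with CESM (50/0.5 = 100), so n = 50 is the planned ceiling. MRI goes only to women for whom it is standard practice and surgical histopathology is also required, so the real n will probably be lower; n = 25 is an assumption. In these scenarios the open range is about as large as sampling error, or smaller.

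**The case against.** **The synopsis sentence is a specific exception to a general rule, and the specific rule governs.** That is a fair reading and may be what was meant. But 8.2, 8.4 and 10.2 do not carry it, and 10.2 labels the plot as histopathology while admitting these women. If primary drug therapy instead means no surgery, the sentence sets a size reference for women whom 10.2 leaves out. The passages need reconciling on either reading.

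**Carrying the exception into the later sections would also remove the ambiguity.** It would. It would also put two different kinds of reference into one agreement plot, one of them visible to the readers.

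**The list of plots belongs in the SAP.** The SAP is not at hand and could add the third plot. Section 10.2 does not rule it out, and the data are already required. This stands and keeps the second part small. What remains is that 10.2 lists the pairs and leaves out one that the endpoint needs.

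**Stronger readings that a reader might infer, and that the documents do not support:**

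- *That the mammogram reference favours CESM.* CESM does create a standard mammographic image, but that is not the initial diagnostic mammogram. Both sets of readers have the mammogram, and the cited study found differences from both techniques.
- *That a CESM–MRI disagreement could not be traced to either technique.* The analysts will hold all three sizes for each woman, and the CESM–histopathology plot shows CESM's error directly. Only a reader limited to the two plots lacks MRI's limits.
- *That the cited studies contradict each other on size agreement.* One is summarised by accuracy of extent and the other by correlation. The second also found no significant difference between CESM and MRI.
- *That core-biopsy sizes would enter the analysis.* Section 10.2 already requires surgical histopathology, so this is a wording conflict only.

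**Conclusion.** Both parts hold on the text, and both are minor. The Protocol gives two size references for a woman who has drug therapy before surgery, and neither is satisfactory for her. Section 10.2 also names one agreement plot fewer than its size endpoint calls for, and MRI's limits of agreement cannot be recovered from the two it names.

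The matter concerns one component of a secondary endpoint in a pilot. The effect of the first part cannot be computed, because the Protocol does not give the number of women treated and then operated on, or how far their two reference sizes would differ. The millimetre figures for the second part rest wholly on assumed SDs and correlations. They show that the limits are not determined, not that the gap is large compared with sampling error.

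**What to change.** 1. Reconcile the synopsis sentence on primary drug therapy with the synopsis endpoint and sections 8.2, 8.4 and 10.2. State that the size-accuracy analysis uses surgical histopathology only, in women who had no drug therapy before surgery. Mammogram and core-biopsy sizes would then not enter it.
2. Report women treated before surgery separately, with CESM–MRI size agreement only.
3. In 10.2, add an MRI–histopathology Bland-Altman plot with limits of agreement, in the same women as the CESM–histopathology plot.

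The cost is some rewording, one separate summary and one further plot, on data that 10.2 already requires. No extra patients or procedures are needed, and clinical management is unchanged. The downside is fewer women in the size-accuracy analysis, by a number the Protocol does not give.

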# **Study Participants**

Women attending CBU who have lesions of suspicion 3, 4 or 5 following routine mammography and ultrasound.

50 patients with successful CESM examinations will be required to establish the technique, study procedures and to provide sufficient data to inform further study. It is estimated, due to randomisation procedure, approximately 100 patients will need to be recruited in order to obtain this number.
Recruitment to the study is planned to run for 12 months or until sufficient number of participants has been accrued. The study will end once data analysis is complete.
To assess the impact the addition of CESM has on patient management.
To compare the sensitivity and specificity of CESM with MRI.
The detection of additional disease by CESM that changes patient management. Analysis will be undertaken to determine the impact of CESM on patient management decisions (actual or hypothetical). These will be extracted from details recorded on the proforma.
Secondary endpoints are the sensitivity and specificity of CESM and MRI on a per lesion basis – including comparison of the maximum dimension of the index tumour – as assessed by independent readers and compared with surgical histopathology.
The efficacy of each technique at detecting additional lesions and the number of false positives identified by each will also be determined. False positives will be confirmed through follow up at 6 months.
Analysis of results will inform further study, e.g. sample size and power calculations, and will include an assessment of clinical technique and study procedures from staff questionnaires.

#### 6. BACKGROUND AND RATIONALE

The advent of digital mammography has presented opportunities for new technologies and techniques to be developed within the field of breast disease diagnosis. One such technology is Contrast Enhanced Spectral Mammography (CESM).

CESM is a technique intended for use as an adjunct following inconclusive mammography and ultrasound examinations. Contrast enhanced images are produced using an x-ray specific contrast media (dye) commonly used for CT scans which is injected intravenously into the patient's arm. A conventional mammography machine – similar or the same as the one on which a woman's initial mammogram would have been taken - is modified to take two images at different x-ray exposures in each of the four standard mammographic views (RCC, RMLO, LMLO, LCC). The first exposure is low energy and the second is high energy. The fully automated procedure creates a standard mammographic image and also produces a contrast enhanced image in exactly the same position with the background subtracted out. This reduces image noise and helps to highlight lesions. The whole procedure from injection of contrast media to production of images takes less than 10 minutes.

Potentially, clinical applications for this technique include clarification of mammographic equivocal lesions, detection of occult lesions and determination of extent of disease. Published studies also indicate that contrast enhanced mammography could play an important role in imaging breasts where dense overlapping tissue can present difficulties when viewing standard mammograms (1,2).

### Summary of literature

There are few published studies comparing diagnostic accuracy of CESM with MRI in patients with newly diagnosed breast cancer. Most published data are a small sub-study of investigations comparing CESM with conventional mammography and/or ultrasound. Studies generally report detectability, multi-focality, correct diagnosis and compare size measurement for extent of tumour against surgical histopathology. Badr et al (3) discussed the implementation of CESM into routine clinical practice. They stated it was easier and quicker to access than MRI but that a disadvantage is being unable to perform a biopsy during the procedure.

Results from two studies comparing mammography plus CESM with mammography plus ultrasound support the view that CESM may be comparable with MRI (4,5). They show CESM improves sensitivity without decreasing specificity, provides a better estimation of extent of tumour and is more effective at demonstrating additional foci than both mammography alone

and mammography plus ultrasound. In 2013 Lobbes et al published a summary on contrast enhanced mammography techniques and studies to date (6). They also concluded contrast enhanced mammography had been shown to be better at detecting breast cancer than mammography - and may be similar to MRI - though MRI may be better for multi-focal disease. Conclusive findings were limited by small study populations and larger studies need to be conducted in order to produce more definitive results.

In a recent study comparing the diagnostic accuracy of CESM with mammography in patients referred from a breast screening programme - which included a cohort of 24 patients who had breast MRI - good agreement was found between tumour size measured by CESM, MRI and histopathology (7). Previous studies comparing assessment of tumour size include a pilot study of 20 patients which showed the correlation between assessed tumour diameters using CESM and histopathology to be good (8) and one in which 142 breast lesions were evaluated by mammography, ultrasound and CESM (5).

Two studies which do directly compare the diagnostic accuracy of CESM with MRI have been reported recently. Jochelson et al studied 52 patients, measuring maximum diameter of the index (main) tumour on imaging (9). Of the 52 lesions, conventional mammography detected 42 and both MRI and CESM detected 50. CESM was accurate for tumour extent in all but 2 index lesions, whereas MRI gave accurate size estimation for all. Jochelson et al concluded that CESM detected known primary tumours at a rate comparable to that of MRI (both 96%) and higher than that of conventional digital mammography (81%). CESM had a lower sensitivity (56%) for detecting additional cancers than MRI (88%), but the specificity was higher. On the other hand MRI found 13 false positive cases, 8 having surgery for ultimately benign change, whereas CESM found 2 false positives, not requiring surgery.

In the second study, Fallenberg et al also reported on the detection of breast cancer and tumour size assessment for CESM compared with MRI (10). They studied 80 patients with newly diagnosed breast cancer of which there was post-op histology for 59. Images were reviewed by an independent reader blinded to other findings. All index tumours (100%) were detected by CESM, 77 (97.4%) by MRI and 66 (82.5%) by conventional mammography. In the correlation of tumour size measurements, there were significant differences between both CESM and MRI compared to mammography. Between CESM and MRI there was no significant difference observed. The best correlation was between CESM and histopathology. There was no evaluation of additional lesions reported.

CESM is a developing technology and the optimum design of equipment and mechanism is still under debate. The addition of digital breast tomosynthesis (DBT) to CESM should further enhance the performance of CESM compared to MRI. Schmitzberger et al (2011) successfully demonstrated the clinical feasibility of CESM DBT as a diagnostic tool but stated

further studies were needed to assess diagnostic sensitivity and specificity (11).

# Rationale

Treatment options for women with proven invasive breast cancer depend on the size of the tumour and the presence and location of any additional disease (12). Breast MRI, using MRI specific contrast media, is currently recognised as the most sensitive imaging technique in determining the extent of disease identified on mammogram or by ultrasound. This means the patient can go straight to definitive surgery rather than having surgical under treatment, i.e. the identification of additional disease may mean the woman has a mastectomy rather than a wide local excision (lumpectomy).

There are several disadvantages of MRI. It is usually performed in a different department from mammography and ultrasound, which can pose problems with accessibility and may delay patient care. Image acquisition takes an average of 40 minutes and the whole procedure can take up to 90 minutes. MRI is also known to produce a higher frequency of false positives than conventional mammography and this can lead to unnecessary surgery and patient anxiety. Some patients may be excluded from undergoing MRI due to claustrophobia or presence of metal within their body. In the UK, MRI is currently used selectively, based on NICE guidelines (13). There are also economic considerations - MRI is expensive.

CESM is being heralded as a diagnostically comparable, less labour-intensive and cost effective technique to breast MRI. Like MRI, CESM can be used to identify lesions not seen on mammography or ultrasound and to assess the size of lesions and stage of disease. The procedure can be performed on the same day using the same equipment and in the same department as a woman's initial clinic visit. This should reduce patient anxiety and has the potential of a definitive decision on patient management being made earlier in the patient pathway. CESM also has the potential to be used as a screening tool in certain groups of women which is not clinically viable with MRI.

The purpose of this study is to refine the CESM technique, assess acceptability of the test and recruitment levels, establish study procedures and examine effect of CESM on patient management decisions. We also hope to demonstrate an increase in sensitivity and specificity compared to MRI. Analysis of results will inform further study, including power calculations. On completion of this project we intend to apply to the UK NIHR Health Technology Assessment Programme for funding to undertake a multicentre trial comparing the diagnostic accuracy of CESM with MRI (perhaps with an extension to CESM DBT if this technique becomes available and minimally proven in terms of clinical performance and workflow).

